9 EFFICACY ANALYSIS

Unless otherwise stated, efficacy analyses will be performed on both the mITT and PP populations (see Section 5 of this SAP).

Tumor measurements based on physical examination will occur at baseline and on the first day of each treatment cycle. Tumor assessments will be made by CT/MRI/Physical Exam prior to dose initiation, at the first protocol-specified tumor measurement evaluation at the end of Cycle 2 and then every 2-3 cycles, and at End of Treatment.

In Part 1, FDG-PET scans were performed at investigator discretion based on totality of additional available data for the subject.

RECIST

Imaging will be performed on the abdomen, chest, pelvis and the site of the primary tumor if elsewhere. The same imaging modality used for an individual patient (i.e., CT or MRI) at Screening should be maintained throughout the study. The findings will be assessed according to the Response Evaluation Criteria in Solid Tumors (RECIST version 1.1).

The response criteria in evaluation of target lesions are defined as follows:

- Complete Response (CR): Disappearance of all target lesions. Any pathological lymph nodes (whether target or non-target) must have reduction in short axis to < 10 mm.
- Partial Response (PR): At least a 30% decrease in the sum of diameters of target lesions, taking as reference the baseline sum diameters.
- Progressive Disease (PD): At least a 20% increase in the sum of diameters of target lesions, taking as reference the smallest sum on study (this includes the baseline sum if that is the smallest on study). In addition to the relative increase of 20%, the sum must also demonstrate an absolute increase of at least 5 mm. (Note: the appearance of 1 or more new lesions is also considered progression).
- Stable Disease (SD): Neither sufficient shrinkage to qualify for PR nor sufficient increase to qualify for PD, taking as reference the smallest sum diameters while on study.

The number and percent of patients with each tumor response will be tabulated using the PP Population by study part, dose level/treatment group, and study visit. Bar graphs of genetic information (BRAF, FGFR3, etc.) leading to target lesion response and best overall response will also be presented.

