The classic 3 + 3 design will be conducted as follows. Initially, 3 patients will be enrolled to a cohort; the occurrence of a single drug-related DLT in one of these 3 patients will prompt enrollment of up to an additional 3 patients to that same cohort i.e., 3 + 3. When more than 1 DLT occurs in  $\leq$  6 patients in a dosing cohort, dose escalation will be stopped and this dose level will be identified as the non-tolerated dose. Doses between the non-tolerated dose and the preceding lower dose, where  $\leq$  1 DLT occurred, may be explored to define the MTD. This strategy allows for a rigorous determination of MTD, especially if the dose increase that resulted in determination of the non-tolerated dose is relatively large (i.e.,  $>$  50%).

At any time during the study, the Sponsor and Investigators may request that cohorts should be enlarged or that exploration of intermediate doses between 2 planned escalation steps should be explored. Such requests will be discussed with the Sponsor and Medical Monitor, and should be based on all data existing at that time, including determinations of pharmacokinetics, pharmacodynamics, and cumulative toxicity. Before each escalation, investigators will be consulted to ensure that all involved agree with the escalation decision.

In addition, once the RP2D is defined, intra-patient dose escalation to the RP2D will be allowed after a patient has completed at least 1 cycle at their assigned dose and only if the patient has experienced no toxicity above Grade 1, upon request by the PI and discussion with the Medical Monitor and the Sponsor.

Part 2 – Cohort-expansion Phase: Additional patients with particular tumor types and/or cancers harboring specific genetics will be recruited for treatment at the Recommended Phase 2 Dose (RP2D). Patients must have measurable disease by RECIST 1.1. Patients will receive twice daily oral doses of BVD-523 in 21-day treatment cycles until disease progression, unacceptable toxicity, or another withdrawal criterion is met (Section 7.2). Treatment cycles will occur consecutively without interruption except when necessary to manage toxicities.

Total enrollment for Part 2 is targeted at approximately 105 evaluable patients. Patients will be enrolled into 1 of 7 treatment groups. Group assignments are made according to the following disease characteristics, which correspond to specific inclusion and exclusion criteria for Part 2.

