## **4 SELECTION OF PATIENTS**

### **4.1 NUMBER OF PATIENTS**

In this Phase 1 study up to 40 patients with advanced solid tumors will be enrolled in Part 1. One to six patients per treatment cohort will be assigned to receive sequentially higher oral doses of BVD-523.

The purpose of Part 2 of this first in human research is to document that there is some evidence of a response. Upon completion of Part 1 of this study, up to approximately 105 evaluable patients with certain cancer types and/or characterized genetics will be assigned to 1 of 7 treatment arms and treated with the RP2D determined in Part 1 (which may be the same or lower than the MTD). The observation of DLTs in more than 33% of patients in any Part 2 cohort with at least 6 patients enrolled at any time during Part 2 will trigger temporary stopping of patient enrollment and revision of the definition of the MTD and potentially RP2D in the specific cohort. Subsequent patients will be treated with a dose lower than the initial MTD and this dose will be determined in discussion with the Clinical Investigators, the Medical Monitor, and the Sponsor.

Enrollment of up to 15 evaluable patients in each cohort provides an 80% probability of seeing at least one positive response if the true response rate is at least 10%. Allowing for a low response rate in these patient cohorts is appropriate based on unmet medical need.

In Part 2 of the study, patients who withdraw at any time preceding the 1st protocol-specified tumor measurement evaluation at the end of Cycle 2 (except for study drug-related AE) will be replaced.

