5.2 MODIFIED INTENT-TO-TREAT

The modified Intent-To-Treat (mITT) Population is defined as all patients receiving at least one dose of study medication. Subject demographics, disposition, and analysis population summaries will be tabulated using the mITT population.

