5.3 PER-PROTOCOL

The Per Protocol population consists of all patients from the modified ITT Population who have completed the first protocol-specified tumor measurement evaluation (except for study drug-related AE) without major protocol violations. All protocol deviations will be reported, but prior to generating TFLs for either Part 1 or Part 2, the list of protocol deviations will be reviewed and each classified as either major or minor. This population will be used to summarize clinical effects on tumor response using RECIST version 1.1 criteria. Analyses based on the PP population will be exploratory.

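### Every planned tumor response display uses the exploratory per-protocol set, so no all-treated response table is planned and reported response rates are likely too high by an unknown amount

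*SAP*

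**What the plan says.** SAP Section 9 gives a default with room for exceptions: "Unless otherwise stated, efficacy analyses will be performed on both the mITT and PP populations". The only response tabulation it goes on to describe names one population: "The number and percent of patients with each tumor response will be tabulated using the PP Population".

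The population definitions point the same way. SAP 5.2 defines mITT as everyone who received at least one dose and lists its uses: "Subject demographics, disposition, and analysis population summaries will be tabulated using the mITT population". Response is not among them. SAP 5.3 limits PP to mITT patients "who have completed the first protocol-specified tumor measurement evaluation (except for study drug-related AE) without major protocol violations". Of PP it says "This population will be used to summarize clinical effects on tumor response using RECIST version 1.1 criteria", and then "Analyses based on the PP population will be exploratory".

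SAP Section 14 labels every efficacy display as PP: seven tables in Part I (14.2.1 to 14.2.7), and seven tables (14.2.1 to 14.2.5, 14.2.7, 14.2.8) and two figures (14.2.1, 14.2.6) in Part II.

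On the protocol side, Section 3.1.2 sizes Part 2 in evaluable patients: "Total enrollment for Part 2 is targeted at approximately 105 evaluable patients". Sections 4.1 and 7.2 replace Part 2 patients who withdraw before the first tumor evaluation at the end of Cycle 2. The one exemption is a drug-related adverse event ("except for study drug-related AE) will be replaced"). Section 7.2 lists disease progression among the reasons for withdrawal.

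**The concern.** Each exception is formally allowed by the wording of the default, but together the exceptions leave nothing for mITT to do. Tumor response is a secondary endpoint in both documents, yet its only planned tables rest on a population the SAP labels exploratory.

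The choice of denominator matters because membership of PP depends on what happens after treatment starts. A Part 2 patient withdrawn for early progression is replaced under Protocol 4.1 and 7.2 and may appear in no response table. SAP 5.3 does not say whether a tumor assessment made before the end of Cycle 2 would keep that patient in PP. SAP 9 gives no rule for treated patients with no post-baseline assessment. The abbreviation for not evaluable is defined in the SAP and may be used in the separate table shells, which were not available for this review.

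The aim of Part 2 (Protocol 4.1, SAP 4) is to show whether there is any sign of response. The tabulated percentages are what readers will take from it.

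**Working it through.** **Display count.** Part I has 7 tables, all PP. Part II has 7 tables and 2 figures, all PP. The total is 7 + 7 + 2 = 16 on PP and 0 on mITT. Six of these are the overall and best overall response tables: Part I 14.2.4, 14.2.5 and 14.2.6; Part II 14.2.4, 14.2.5 and 14.2.7.

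**The plan's own figure.** Protocol 4.1 states an 80% chance of at least one response among 15 evaluable patients at a true rate of 10%. The check is 1 − 0.9^15 = 0.794, which agrees with the stated figure and is not in dispute.

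**Effect of the denominator.** Let d be the share of treated patients lost unassessed before the end of Cycle 2, all of them non-responders. Let a be the share of those losses kept in PP through the drug-related-AE exception. With no other exclusions,

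PP rate = all-treated rate / (1 − d(1 − a)).

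The documents give neither d nor a; the values below are assumed. For an all-treated rate of 10%:

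| d | a = 0 | a = 0.5 | a = 1 |
|---|---|---|---|
| 10% | 0.10/0.90 = 11.1% | 0.10/0.95 = 10.5% | 10.0% |
| 20% | 0.10/0.80 = 12.5% | 0.10/0.90 = 11.1% | 10.0% |
| 30% | 0.10/0.70 = 14.3% | 0.10/0.85 = 11.8% | 10.0% |

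**Patients missing from every response table.** If the Part 2 PP set reaches the 105 evaluable patients in Protocol 3.1.2, the number of further treated patients outside it is 105/(1 − d(1 − a)) − 105:

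- a = 0: 11.7, 26.3 and 45.0 for d = 10%, 20% and 30%
- a = 0.5: 5.5, 11.7 and 18.5
- a = 1: none

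SAP 4 states up to 105 additional patients without the word evaluable. If 105 is the number treated, the a = 0 figures become 105 × d = 10.5, 21 and 31.5. All of these shrink if an earlier assessment counts toward PP.

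**One Part 2 group, 15 patients in PP and 3 responders.** The PP rate is 3/15 = 20.0%.

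- Four other patients lost and replaced: all-treated 3/(15 + 4) = 3/19 = 15.8%.
- Two lost and replaced, with two drug-related-AE losses already among the 15: all-treated 3/(15 + 2) = 3/17 = 17.6%.

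**Opposite direction.** Suppose 15 are treated, all are assessed, and the only responder is a major violator. PP gives 0/14 = 0%; all-treated gives 1/15 = 6.7%.

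**The case against.** The strongest counter-argument is that this is a mismatch in a display list. The PP sentence in SAP 9 concerns response by study visit, and best overall response has no visit dimension, so the default could still govern it. Section 14 has other labelling slips, such as duplicated table numbers and pharmacodynamic tables assigned to the pharmacokinetic population. This reading does not survive SAP 5.3, which gives tumor response in general to PP, or the uniform PP label on the best overall response tables.

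A second argument is that few patients would be lost unassessed. Both documents schedule a tumor assessment at end of treatment and physical-examination tumor measurements on the first day of each cycle (Protocol 6.8, SAP 9). This could well reduce the losses. It does not settle who is in PP, because PP is tied to completing the first scheduled evaluation and SAP 5.3 is silent on earlier assessments.

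A third argument is that PP reporting follows from sizing Part 2 in evaluable patients and replacing early withdrawals. Dropping unassessed non-responders also leaves the count of responders unchanged, so it cannot create or hide evidence of response. Both points stand. They justify keeping the PP tables and limit the consequence, but the percentages still change, and excluding a responder for a major violation can hide evidence.

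The plan also makes no inferential use of the rate (Protocol 10.3.6, SAP 6.5). The listings (SAP 6.6) and population counts (SAP 8.1) allow an all-treated rate to be rebuilt by hand. In Part I, dose cohorts of one to six patients make any percentage weak. These points limit the seriousness; they do not supply the missing table.

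**Conclusion.** The concern holds. As written, the plan produces no response table on all treated patients, and the mITT default in SAP 9 has no effect. That conclusion rests on the text and the display list and needs no assumption beyond the unseen table shells following that list.

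The direction of bias is likely upward, since patients lost before any assessment are non-responders, but it is not certain. The size is unknown. Under the assumed losses of 10% to 30%, a 10% all-treated rate would show as anything from 10.0% (all losses kept in PP) to 14.3% (none kept). The change should be made, but its importance is moderate: the result is descriptive and can be reconstructed from planned output.

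**What to change.** - Add mITT versions, on the SAP 5.2 definition of at least one dose, of Part I Tables 14.2.4 to 14.2.6 and Part II Tables 14.2.4, 14.2.5 and 14.2.7.
- In those tables show patients with no post-baseline assessment as not evaluable and keep them in the denominator as non-responders. This classifies missing assessments and does not impute a measurement, so it is compatible with SAP 7.1.2.
- Keep the PP tables as the exploratory supplement.
- State in SAP 5.3 whether a tumor assessment before the end of Cycle 2 counts toward PP membership.
- Reconcile SAP 5.2, 5.3, 9 and 14. SAP 15 describes mITT as all enrolled subjects; align it with the dosed-patient definition in SAP 5.2 so that the denominator is unambiguous.

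The cost is some SAP wording and six repeated tables on a population that already exists; no new data are needed. Reported response rates are likely to be slightly less favourable.

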10 SAFETY

Safety analyses will be performed using the Safety Population. Safety will be assessed by examining all adverse events reported during the study including the incidence, and relationship to BVD-523. In addition, safety evaluations will be conducted at Screening, Baseline, Days 8, 15, 22, 29, 36, 43, and, in patients who continue treatment, every 3 weeks or if clinically indicated thereafter. These evaluations will include a physical examination, ECOG performance status, vital signs, and clinical laboratory evaluations (hematology,

chemistry, urinalysis and pregnancy test). Electrocardiography measurements will be collected in Cycle 1 (determined by ECG at Screening and Day 8 and 12±2 hours Holter monitoring during PK sampling days). Patients with a normal ECG in Cycle 1 need not have repeat ECGs in subsequent cycles. An ophthalmologic assessment will also be conducted at screening, at the end of study and at other visits by an ophthalmologist if clinically indicated. Additionally, subjects will be asked to return for a 30 day safety visit (or earlier if subsequent therapy is initiated prior to 30 days) or contacted by phone after the last dose of study medication is taken.

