### 7.2 EARLY DISCONTINUATION OF INDIVIDUAL PATIENTS

Patients are to be withdrawn from the study for any of the following reasons:

- Withdrawal of informed consent
- Disease progression (at the discretion of the PI). However it is particularly important in patients for which FDA approved BRAF and/or MEK inhibitors are indicated that BVD-523 treatment NOT be continued beyond tumor progression.
- Unacceptable toxicity
- Changes in the patient's condition render the patient unacceptable for further treatment in the judgment of the PI
- Patient non-compliance as assessed by the investigator
- Patient has a positive serum pregnancy test (withdrawal is required)
- Patient is lost to follow-up

Patients will also to be withdrawn at any time if the investigator concludes that it would be in the patient's best interest for any reason. Protocol violations do not lead to patient withdrawal unless they constitute a significant risk to the patient's safety.

Patients can voluntarily withdraw from the trial for any reason at any time. They are to be considered withdrawn if they state an intention to withdraw, fail to return for visits, or became lost to follow up for any reason.

In Part 1 of the study, patients who withdraw at any time preceding the last visit of Cycle 1 (Day 22) will constitute an early discontinuation and must be replaced in order to ensure proper data accrual for dose escalation decisions. A patient who experiences a DLT in Course 1 and withdraws before Day 22 either because of the toxicity or otherwise, will nonetheless have that DLT counted in the assessment of potential cohort expansion and/or dose escalation (see Table 3.2).

In Part 2 of the study, patients who withdraw at any time preceding the 1st protocol-specified tumor measurement evaluation at the end of Cycle 2 (except for study drug-related AE) will be replaced.

The investigator must determine the primary reason for a patient's withdrawal from the study and record this information on the eCRF.

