3 STUDY DESIGN

3.1 OVERALL STUDY DESIGN

This is an open-label, multi-center Phase 1 study to assess the safety, pharmacokinetics, and pharmacodynamics of escalating doses of BVD-523 in patients with advanced malignancies. It will be conducted at up to 15 sites. This clinical study comprises 2 parts: Part 1: Dose-escalation Phase and Part 2: Cohort Expansion Phase.

Part 1: Dose-escalation Phase, An accelerated dose escalation plan will be used to establish DLT, MTD, and the RP2D. One to 6 patients per treatment cohort will be assigned to receive sequentially higher oral doses of BVD-523 on a twice daily schedule (b.i.d.) for 21 days (a “Cycle”), starting at a dose of 10 mg twice daily. Patients will receive twice-daily oral doses of BVD-523 until disease progression, unacceptable toxicity, or a clinical observation satisfying another withdrawal criterion is noted. Treatment cycles will occur consecutively without interruption, except when necessary to manage toxicities. Up to 40 patients will be enrolled in Part 1. Patients with advanced-stage solid tumors only (no hematological malignancies) will be enrolled in the dose-escalation phase of the study. The study will initially be conducted as an accelerated single patient cohorts design, followed by a standard 3 + 3 design, informed by the accrued safety experience throughout the study (see Table 1 below). All dose-escalation decisions will be based on Cycle 1 safety data. Patients who withdraw at any time preceding the last visit of Cycle 1 (Day 22) will constitute an early discontinuation and must be replaced in order to ensure proper data accrual for dose escalation decisions. A patient who experiences a DLT in Course 1 and withdraws before Day 22 either because of the toxicity or otherwise, will nonetheless have that DLT counted in the assessment of potential cohort expansion and/or dose escalation. Doses will not be escalated unless the patient(s) receiving the highest current dose has been observed for at least 3 weeks. No intra-patient dose escalation was permitted under the original protocol or the first two amendments. Starting under amendment three, intra-patient dose escalations were allowed; see protocol for details.

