5 ANALYSIS POPULATIONS

Five analysis populations will be used to analyze the study data. Below are details of each analysis population:

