5.1 SAFETY

The Safety Population consists of all patients receiving at least one dose of study medication.

This population will be used to summarize demographics and baseline characteristics, previous and concomitant medication/therapies, treatment exposure and all safety endpoints including AE, physical examination (PE), ophthalmology examination, clinical laboratory tests (chemistry, hematology, and urinalysis), serum/urine pregnancy test, ECG, Holter monitoring, and vital signs (VS).

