6.6 STATISTICAL NOTATION AND METHODOLOGY

Unless stated otherwise, the term “descriptive statistics” refers to the number of patients (n), mean, median, standard deviation (STD), minimum (Min), and maximum (Max) for continuous data and frequencies and percentages for categorical data. Min and Max values will be presented using the precision of the original value, means and medians will be rounded to 1 decimal place greater than the precision of the original value, and STDs will be rounded to 2 decimal places greater than the precision of the original value. Percentages will be rounded to the nearest whole number. For percentage values that are less than 1% but greater than 0%, they will be presented as “< 1%”. Similarly, “> 99%” will be used to display percentages that are greater than 99% but less than 100%. P-values will be presented with 3 decimal places and values less than 0.001 will be presented as < 0.001.

All data collected during the study will be included in data listings and will be displayed and sorted by study part, dose level, cohort/treatment group, patient number and then by date/time (including visit, cycle, and day), if any, for each patient number, unless otherwise noted.

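### The Part 1 DLT table uses all dosed patients, so replaced patients can dilute the DLT proportion below the MTD cut-off, and exactly one-third of patients (2/6) is classed inconsistently

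*SAP*

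**What the plan says.** **Definition of the MTD.** Protocol 3.1.4.1 and SAP 2.1.1 and 10.2 define it as the highest dose at which no more than 33% of patients have a related DLT in the first 21 days.

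**Count rule.** Protocol 3.1.2 says that with more than one DLT in six or fewer patients, "dose escalation will be stopped and this dose level will be identified as the non-tolerated dose". SAP 3.1 repeats the rule.

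**Replacement.** SAP 3.1 says: "Patients who withdraw at any time preceding the last visit of Cycle 1 (Day 22) will constitute an early discontinuation and must be replaced". Protocol 7.2 gives the reason: such patients "must be replaced in order to ensure proper data accrual for dose escalation decisions". Both documents add that a DLT in a patient who leaves early still counts.

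**Population.** SAP 10 says: "Safety analyses will be performed using the Safety Population". SAP 5 says "Five analysis populations will be used to analyze the study data": Safety, mITT, per-protocol, PK and PD. None is a DLT-evaluable set. SAP 5.1 says "The Safety Population consists of all patients receiving at least one dose of study medication". SAP 14 places Part I Table 14.3.1.1 on that population.

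**Display.** The SAP 6.6 default is "frequencies and percentages for categorical data", and "Percentages will be rounded to the nearest whole number". SAP 14 says the table shells are separate documents, so the layout of Table 14.3.1.1 cannot be seen.

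**Use.** SAP 12 plans a Part 1 analysis to support the MTD and RP2D discussions. DLTs and the MTD are primary endpoints (SAP 2.3.1).

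**The concern.** The escalation rules and the DLT table use different denominators. For escalation, a patient who leaves in Cycle 1 without a DLT is uninformative and is replaced. In the Safety Population the same patient stays in the denominator as someone who had no DLT. No text removes such patients from Table 14.3.1.1, and the effect runs one way: it can only lower the displayed proportion.

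A second problem does not depend on replacement. The MTD definition is a percentage and the non-tolerated rule is a count, and they meet at 2 DLTs in 6 patients. By count, that dose is non-tolerated. If 33% is shorthand for one-third, the same dose satisfies the MTD definition. If 33% is literal, 33.3% exceeds it, but the whole-number display prints 33%.

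At stake is the reported DLT proportion for a primary endpoint, which may seem to contradict the dose decision it accompanies.

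**Working it through.** **1. Do the cut-off and the count rule agree on the escalation denominators?** Take every outcome with at least 2 DLTs in at most 6 patients. The smallest proportion is 2/6 = 33.33%; the next is 2/5 = 40%. Read literally, every non-tolerated outcome exceeds 33%, so the two rules agree. Read as one-third, they disagree at 2/6 only.

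**2. Effect of rounding alone.** 2/6 prints as 33%. No other non-tolerated outcome with 6 or fewer patients prints at or below 33%.

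**3. Effect of the denominator alone.** With k DLTs in n evaluable patients and r replaced patients without a DLT, the Safety Population proportion is k/(n + r).

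- 2/6 with r = 1: 2/7 = 28.6%. With r = 2: 2/8 = 25.0%.
- Smallest r giving an unrounded value of 33% or less: 2/6 needs 1; 2/5 needs 2; 2/4 needs 3; 2/3 and 3/6 need 4; 3/3 and 4/6 need 7.

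**4. How often?** The documents give no drop-out rate and no DLT rate, so both are assumptions. Let p be the true DLT rate and d the chance of leaving in Cycle 1 without a DLT and being replaced. Three evaluable patients are treated; 1/3 expands towards six; a second DLT stops escalation. The added three enrol either together or one at a time. The number replaced before the n-th evaluable patient is negative binomial.

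Chance that a cohort ends at exactly 2/6:

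- together: [3p(1 − p)²]²
- one at a time: 3p²(1 − p)⁴

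| p | 10% | 20% | 33% | 50% |
|---|---|---|---|---|
| Together | 5.9% | 14.7% | 19.8% | 14.1% |
| One at a time | 2.0% | 4.9% | 6.6% | 4.7% |

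Both expressions peak at p = 1/3, so the 33% column is close to the maximum.

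Worked case, p = 0.33, d = 0.10, enrolled together:

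- 2/6: 0.1975 × (1 − 0.9⁶) = 0.1975 × 0.4686 = 0.0925
- 3/6 with at least 4 replaced: 0.0973 × 0.0083 = 0.0008
- 2/3 with at least 4 replaced: 0.2189 × 0.0013 = 0.0003
- total 0.0936

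Cohorts stopped by the count rule but showing 33% or less, unrounded, on the Safety Population at d = 0.10:

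| p | 10% | 20% | 33% | 50% |
|---|---|---|---|---|
| Together | 2.8% | 7.0% | 9.4% | 6.8% |
| One at a time | 1.2% | 3.1% | 4.5% | 3.6% |

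Over drop-out of 5%, 10% and 20% at p = 0.33, the figures are 5.2%, 9.4% and 15.8% together, and 2.1%, 4.5% and 10.1% one at a time. All are rates per 3+3 cohort, not per trial.

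**5. Does one change suffice?** No. With an evaluable denominator alone, 2/6 still prints as 33%. With decimals alone, 2/7 still shows 28.6%. With both, 2/6 shows as 33.3% and agrees with the count rule only if 33% is literal.

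**The case against.** Several points limit this, and most of them stand.

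- **No decision changes.** Escalation and the non-tolerated call rest on counts (Protocol 3.1.2 and 8; SAP 3.1). The RP2D is set by discussion, in which PK, PD and cumulative toxicity may also weigh. A reader might infer that a non-tolerated dose could be declared the MTD because of this table. The documents do not support that: Part I Table 14.3.1.3 reports the selected MTD directly.
- **The layout is unknown.** The shells are not in the documents, so it is not shown that Table 14.3.1.1 will print a percentage. If it follows SAP 6.6, the frequency appears beside the percentage, which softens the rounding problem. A count of 2 with a column total of 7 would still not show who was replaced.
- **Replaced patients can be traced.** Early withdrawals, exposure and DLTs are all listed (SAP 8.1, 10.1 and Listing 16.2.3.1). That helps a careful reader but does not correct the table.
- **The definition says patients, not evaluable patients.** A dosed-patient denominator therefore does not breach its wording. The mismatch is with the replacement rule.
- **Timing.** SAP 15 says that the Part 1 SAP was finalised under amendment 4, so the MTD and RP2D discussion may be over. What remains is the final report.

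It would also be an overstatement to cite 20% of cohorts as the expected rate of a printed conflict. That figure is near the peak over p, assumes that the added patients enrol together, and concerns 2/6 on rounding alone.

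**Conclusion.** The point holds as a minor reporting issue on a primary endpoint. If Table 14.3.1.1 shows percentages, replaced patients can only lower them, and one replaced patient takes 2/6 = 33.3% to 2/7 = 28.6%. At an assumed 10% drop-out, a stopped cohort shows 33% or less, unrounded, in roughly 3% to 9% of cohorts (added patients together) or 1% to 5% (one at a time), for true DLT rates between 10% and 50%. The 2/6 and 2/7 arithmetic needs no assumed rates; the frequencies do.

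Separately, the percentage definition and the count rule leave exactly one-third unsettled. A new population and a new display do not resolve that unless 33% is meant literally. The Part 2 enrolment trigger, set at more than 33% (Protocol 4.1), has the same ambiguity at 2/6, 3/9, 4/12 and 5/15.

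**What to change.** 1. Add a DLT-evaluable population to SAP 5: patients with a DLT in the first 21 days, or who completed the Cycle 1 DLT observation period. State whether completion means 21 days observed or attendance at the Day 22 visit. Use it as the denominator for any DLT proportion in Part I Table 14.3.1.1 and in the SAP 12 analysis, with the Safety Population proportion alongside if wanted. Other adverse event tables stay as they are.
2. Exempt DLT results from the SAP 6.6 rounding rule and show k/n with at least one decimal.
3. The sponsor should reconcile the ≤33% MTD definition, the 3+3 count rule and the Part 2 trigger, and state how exactly one-third is classed and which rule governs. This review does not say which is right.

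The cost is one population flag and some SAP wording, with no new data. The reported DLT proportion may be slightly higher, because partly observed patients without a DLT are left out while early DLTs are kept. Showing both denominators makes that visible.
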